Appendix 4: National Institutes of Health Stroke Scale (NIHSS)

Investigators at the University of Cincinnati Stroke Center developed the NIHSS by quantifying the neurological functional status of stroke patients.

Overview

Comparisons between the baseline assessment and the assessment at 3-month follow-up of acute stroke patients should be conducted by the same assessor.

Instructions for use: Assessments must be conducted by investigators holding a NIHSS usage certificate.

The examination should be conducted in the order of items on the scale. Record the results after completing each item and avoid revisiting previous items to change scores. Follow the guidelines for each examination. The score should reflect what the patient has done, not what the clinician believes the patient can do. The doctor should examine and record simultaneously for a rapid assessment. Do not instruct the patient on how to do, meaning not allowing the patient to repeat your instructions, thereby showing improvement with each repetition, and affecting the accuracy of the score.

For all examination items, except for the "Language Function" sub-item, record the patient's initial response. Even if subsequent responses may be better, they should not be used; In item 7 "Ataxia", "one limb" refers to either an upper limb or lower limb, meaning each patient has four limbs, not just two on one side. For instance, if a patient exhibits limb ataxia on the right side, the patient should be scored 2 points for having ataxia in two limbs, not 1 point. This is a common misunderstanding in clinical trials in China.

In item 11 "Neglect", clinicians in China often overlook this aspect. The neglect test primarily assesses spatial visual neglect and tactile neglect. Visual neglect can be examined simultaneously with the "Visual Fields" item. If the patient has a severe visual field deficit that hinders visual signal stimulation on both sides, proceed to examine the condition of skin tactile neglect. If it is normal, it is recorded as normal. If the patient is aphasic but can attend to both sides, it is considered normal.

For items that cannot be assessed, please record the score as the pre-defined value, commonly

A Randomized, Double-blind, Placebo-controlled, Multicenter Clinical Study of Tongxinluo Capsule in the Treatment of

Ischemic Stroke

set internationally as "UN" or "9". However, in computer statistical processing, treat "UN" or "9" as the default value.

- Give the score as per table and record the results. Do not change the score, which reflects the actual situation of the patient, rather than what the doctor believes the patient should be. Quickly check and record the results. Do not train the patient unless you have the necessary instructions (e.g., repeatedly asking the patient to make some kind of effort).
- If some items are not assessed, they should be specified in the table.

Text explanation

la Level of consciousness: The investigator selects an answer and gives a score, even if there are difficulties such as endotracheal intubation, language disorders, tracheal trauma, or bandaging. If the patient shows no response (or reflex activity) to strong external stimuli, a score of 3 is given.

Scoring criteria:

- 0—Conscious, able to respond quickly
- 1—Partially conscious, can obey, answer, and respond appropriately to mild stimuli
- 2—Not conscious, requires repeated stimuli to elicit a response or slow response. Requires strong or painful stimuli to elicit a response (not reflexive)
- 3—Only reflexive movements or vegetative effects or complete unresponsiveness, flaccid paralysis, no reflexes

1b Level of consciousness questioning: Requires the patient to answer the current month and their age. The answer must be correct—partial scoring based on approximation is not allowed. Individuals who cannot comprehend the question due to aphasia or unconsciousness are scored 2 points. Patients with severe dysarthria, language disorders, or an inability to speak due to reasons such as tracheal intubation or tracheotomy, or any other cause not secondary to, are scored 1 point. It is crucial to note that scoring is based solely on the initial response, and the examiner must not provide additional

Scoring criteria:

- 0—Correct responses to both questions
- 1—Correct response to a question
- 2—Incorrect responses to both questions.

Ischemic Stroke	
linguistic or non-linguistic cues.	
and close their eyes, and then to grip and release with the unaffected hand. If hand cannot be used, replace it with an alternative command. If the patient has a clear intention to fulfill the request but is unable to do so due to physical weakness, the assessment should reflect this. If the patient does not respond to these requests, the examiner should demonstrate the tasks to them (using gestures), and then score based on the results (e.g., completing 0, one, or both commands). Patients with trauma, recent limb surgery, or other physical impairments should be given a single appropriate command. Draw the corresponding answer based on their initial response.	Scoring criteria: 0—Responsive to both commands 1—Responsive to one command 2—Non-responsive to both commands
2. Gaze: Test only horizontal eye movement function. Score voluntary or reflexive (oculocephalogyric reflex) eye movements, but there is no need for caloric test. If the patient can overcome binocular gaze with voluntary or conditioned reflexes, score 1 point. If the patient has peripheral nerve paralysis (cranial nerves III, IV, VI), still score 1 point. The gaze test is applicable to all aphasic patients. For patients who have undergone ophthalmic surgery, are bandaged, are already blind, or have visual field impairments for various reasons, the examiner should conduct a gaze test through conditioned eye reflex. For example, instruct the patient to fix their gaze on an object and then have them walk from one side to the other, which may reveal partial gaze palsy in the patient.	Scoring criteria: 0—Normal 1—Partial gaze palsy, impaired gaze function in one or both eyes, but not complete paralysis of all gaze abilities 2—Compulsive strabismus or complete gaze palsy that cannot be overcome by oculocephalogyric reflex
3. Visual field: The testing of visual fields (upper and lower quadrants)	Scoring criteria:

involves the examiner having the patient judge the number of fingers or an appropriate object in front of them to assess their visual capacity. If the patient can perceive the direction of moving fingers, it can be considered normal. If one eye is blind, or if one eyeball has been removed, the visual field test should be performed on the other eye. Visual field asymmetry or quadrant blindness is scored 1 point. Bilateral blindness, regardless of the cause, is scored 3 points. Patients with loss of light sensitivity should answer question 11.

- 0-Normal visual field, no hemianopia
- 1—Partial hemianopsia
- 2—Complete hemianopia
- 3—Bilateral hemianopia (including cortical blindness).

4. Facial paralysis:

The examiner gives verbal commands or gestures, asking the patient to show teeth, frown, or close their eyes. For patients with poor response or lack of comprehension, judgment is made based on whether facial expressions produced under stimulation are symmetrical. If there is facial injury, bandaging, a tracheal strap, or other physical disorders hindering facial expressions, they should be moved aside as much as possible.

0—Able to make facial expressions normally

- 1—Slight paralysis (nasolabial fold becomes shallow, asymmetry on both sides when smiling)
- 2—Partial paralysis (lower half of the face completely or nearly completely paralyzed)
- 3—One or both sides of the face completely paralyzed (no facial expressions can be made on the upper and lower face)

5 & 6. Upper and lower limb motor function:

Place the four limbs in the appropriate position, extending the arms (palms down) at a 90 degree angle from the body (if sitting) or at a 45-degree angle (if lying down), and extending the legs at a 30 degree angle from the body (if lying diagonally). If the arms can be held for more than 10 seconds and the legs for more than 5 seconds, a judgment can be made based on this condition. For aphasic patients without other stimuli, encouragement through language or gestures can be used to help them complete the movement of the arms and legs. Begin by testing the non-paralyzed arm, and then alternate with the other limbs. If the patient has an amputation or

- 0—The arms remain at 90 degree or 45 degree without movement for 10 seconds
- 1—Shaking observed; although the arm could be maintained at 90 degree or 45 degree, there is some shaking before the full 10 seconds, and it does not fall to the bed or other support.
- 2—Although able to lift the arm against gravity, it cannot be maintained at 90 degree or 45 degree and quickly fall back to the bed
- 3—Arm is unable to lift against gravity

		
joint fusion at the shoulder or hip joint, it should be recorded as	4—No response	
unable to test (marked as UN or a predetermined value such as "9"),	Unable to test (marked as UN or a predetermined	
and the reason should be specified.	value such as "9") = Amputee or individuals	
	with joint fusion at the shoulder or hip joint	
5a: Left arm	0—The leg can be maintained at 30 degree	
5b: Right arm	without shaking for 5 seconds	
	1—Shaking observed; the leg can be maintained	
6a: Left leg	at 30 degree, but it moves downward before	
6b: Right leg	reaching 5 seconds, without falling to the bed or	
	other support	
	2—The patient has strength to lift the leg but	
	cannot maintain it at 30 degree, and when	
	putting down, seek support from the bed or	
	another surface	
	3—The patient has no strength to lift the leg; the	
	leg immediately falls onto the bed	
	4—No response	
	UN or "9" = Amputee or individuals with joint	
	fusion at the shoulder or hip joint	
7. Ataxia:	Scoring criteria:	
This item tests the degree of impairment in unilateral cerebellar	0—No ataxia	
function. During the test, keep both eyes open. If there is visual	1—Ataxia on one side of the body	
impairment, ensure testing is done within the intact visual field.		
Perform the finger-to-nose test and heel-knee-tibia test on both	2—Ataxia on both sides of the body	
sides. Unless the arm is extremely weak during testing, assess for	Cannot be tested = Amputation or joint fusion	
ataxia in all other cases. If the patient cannot comprehend or has		
limb paralysis, record as 0 points. If the patient is an amputee or has		
joint fusion, it should be recorded as untestable, with the reason		

specified. Testing blind patients involves lightly touching their nose with a finger to determine if there is any ataxia.

8. Sensation:

Inspect for the sensation and painful expression caused by needle pricks; observe for avoidance of noxious stimuli in comatose or aphasic patients (muscle contraction). If there is no sensation, it is pathological; only sensory loss caused by stroke is considered abnormal. To accurately assess complete sensory loss throughout the body, it is important to involve as many body regions as possible. The examiner should accurately test certain areas of the patient's body, such as the arms (not just the hands), legs, trunk, and face, to determine whether there is a loss of sensory function on one side of the body. "Severe or complete sensory loss" refers to patients with significantly impaired or completely lost sensory function, scored 2 points; comatose or aphasic patients may also be scored 1 or 0 points; brainstem stroke patients with bilateral limb sensory loss are scored 2 points; if the patient shows no response at all or has quadriplegia, a score of 2 is given; comatose patients (scored 3 points in 1a) should be scored 2 points.

Scoring criteria:

0—Normal; No sensory loss

1—Mild to moderate sensory loss; the patient has a delayed response to needle pricking or lacks pain sensation on the affected side, and only being aware that the body is being touched (has tactile sensation)

2—Severe or complete sensory loss; when pricked with a needle on the patient's face, arm, and leg, the patient feels no sensation

9. Language expression ability:

During the testing process, brief greetings can provide information about the patient's language expression ability and condition. The patient is asked to describe what is happening in the picture, give a name to the picture, and read any text present in the picture. The patient's comprehension and language expression abilities can be assessed based on their performance in executing the test commands. If visual issues hinder the test, the patient is asked to distinguish objects placed in their hands through touch. Repeat

Scoring criteria:

0-No Aphasia: Normal

1—Mild or moderate aphasia: Fluent language expression and comprehension with minor thought and grammatical errors. However, due to reduced comprehension and/or language expression ability, it is difficult or impossible to engage in a conversation based on provided materials. Nevertheless, through discussion with

the process multiple times and instruct the patient to verbalize their findings. For patients with tracheal intubation, instruct them to write down the corresponding information. For patients in a coma (as indicated in 1a = 3), record the answer as 3. For patients in a drowsy state or with limited cooperation, the examiner should choose an appropriate score for the patient. However, a score of 3 should only be assigned for patients who cannot speak and cannot execute any commands.

the patient about a particular object, the examiner can infer the specific picture or card the patient is referring to from their responses.

2—Severe aphasia: All expressions consist of disjointed words or phrases. Listeners must exert considerable effort to understand, inquire, and guess. The scope of communication between the patient and others is very limited and challenging. It places a significant burden on listeners, and the examiner cannot discern the specific object the patient is referring to from their responses.

3—Aphasia: Unable to speak or completely aphonic, with no language or auditory, speaking, or comprehension abilities.

10. Dysarthria:

If a patient is able to repeatedly read a specified sentence, they should be considered as having normal speech expression. In cases of severe aphasia, judgment can be made by assessing the patient's unconscious articulation of syllables. If the patient has tracheal intubation or other physical disorders that impede pronunciation, score UN or "9". The examiner must clearly explain why no score is given. Do not tell the patient why they are being tested.

Scoring criteria:

0-Normal

1-Mild to moderate: The patient speaks indistinctly and can articulate some sentences or words intermittently. Although there is some difficulty, the meaning expressed can be generally understood.

2—Severe: The patient's speech is so unclear that it cannot be understood, but there is no aphasia or the aphasia is disproportionate, or there is aphonia.

UN or "9" = Intubation or caused by physical

11. Resolution and inattention (neglect):

The information about neglect has been adequately obtained in the above examinations. If the patient has severe visual impairment to the extent that simultaneous visual stimulation on both sides is not possible, and skin stimulation is normal, it is recorded as normal. If there is aphasia but definite attention to both sides, it is recorded as normal. Spatial neglect or anosognosia can also be considered as evidence. Because only abnormalities are recorded, this item must be measurable.

disorders.

0—Normal

1-Vision, touch, hearing, and spatial stimuli: Able to recognize one of these sensory stimuli when two are presented simultaneously.

2—Almost no sensation when stimulated, with no recognition of one's own hands and spatial orientation

Chinese-adapted words and sentences for assessing speech disorders and dysarthria:

Please read the following words:

Mom

Please read the following sentences:

Know Earth

Go down stairs Airplane, airplane

Go home and cook Silk

[figure not shown]
Review at school Start work on time

Deliver an impressive speech Eat grapes without spitting out the grape

skin

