5.1. Inclusion criteria

- 1. Ischemic stroke within 72 h after onset, confirmed by MRI or CT;
- 2. Age 35–75 years, inclusive;
- 3. Patients with the first attack or patients with stroke history (modified Rankin Scale score 0-1);
- 4. Clear signs of localization of nervous system, NIHSS score 4 to 22;
- 5. Patient or proxy has signed *Informed Consent Form*.

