7.1.2 Secondary efficacy endpoint

1. Improvement in neurological deficit (proportion of patients with NIHSS ≤1 or NIHSS improved by 4 points or more)

- 2. Improvement in activities of daily living (proportion of patients with BI index \geq 85)
- 3. Disability rate (proportion of patients with mRS score \geq 3 points);
- 4. Continuous changes of mRS scores;
- 5. Incidence of ischemic cerebrovascular disease during follow-up;
- 6. Incidence of combined vascular events during follow-up;

7.2 Safety indicators:

- Adverse event assessment
- Clinical laboratory indicators include blood routine (hemoglobin, red blood cells, white blood cells, platelets), urine routine (urine protein, urine white blood cells, urine red blood cells), serum biochemistry (alanine aminotransferase, aspartate aminotransferase, alkaline phosphatase, glutamine, urea nitrogen, creatinine, total bilirubin, blood glucose, total cholesterol, triglycerides, low-density lipoprotein, high-density lipoprotein).
- Coagulogram: Coagulation 4-item (PT, APTT, TT, FIB)
- 12-lead ECG
- Physical examination

8 Study Process

Refer to Table 1 for details of the study process.

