11.4 Randomization

11.4.1 Randomization method

Method of centralized dynamic randomization, with each center competing for enrollment. The centralized randomization procedure will be performed using the Interactive Web-based Randomization System (IWRS) provided by Peking University Clinical Research Institute. The principal investigators at each study center will have their own unique login credentials, ensuring the security and integrity of the login system. After screening each eligible subject at all participating centers in this study, the investigator will log in to the randomization system with their accounts, input relevant information about the subject and obtain the drug packaging number for that subject. The investigators will administer the relevant drug based on the drug

packaging number. Subjects will be randomized into treatment and control groups based on stratification factors, which include:

- 1. Whether thrombolytic therapy has been administered: Yes, No
- 2. NIHSS Score: 4–7 points, 8–14 points, 15–22 points

The randomization method is the Pocock and Simon minimization algorithm. Patients must initiate the study treatment within 24–48 hours after randomization. This study employs non-repeated randomization.

12 Statistical Analysis

After the study protocol is finalized, statistical professionals will collaborate with the principal investigator to develop the statistical analysis plan. The statistical analysis software used is SAS® 9.2 software (Software installation point authorization code: 11202165). The sample size calculation software used is PASS 11.

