4.5.1 Inclusion criteria

- 1. Have onset of ischemic stroke within 72 hours, and be diagnosed by CT/MRI;
- 2. At age of 35to 75;
- 3. First onset or with past history of ischemic stroke, but have recovered before this onset, that is with mRS score <1;
- 4. With clear nervous system orientation sign, and national institutes of health stroke scale (NIHSS) ≥4 and <22:
 - 5. The patient or his (her) legal representative has signed informed consent before the start of study.

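### Appendix 4 scores NIHSS item 7 (ataxia) by limb in its Overview but by body side in its score table, so arm-and-leg ataxia confined to one side is worth 2 points or 1 depending on the page

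*Combined protocol and SAP*

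**What the plan says.** **Overview of Appendix 4.** For item 7, one limb "refers to either an upper limb or lower limb, meaning each patient has four limbs, not just two on one side". The worked example is a patient with limb ataxia on the right side, of whom it says "the patient should be scored 2 points for having ataxia in two limbs, not 1 point". The Overview adds that the one-point reading is a frequent mistake in Chinese trials.

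**Item 7 score table, same appendix.** After 0 for no ataxia, the two levels are "1—Ataxia on one side of the body" and "2—Ataxia on both sides of the body". The general instructions ahead of the items tell assessors to take scores from the table.

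**Where the total is used.**
- Eligibility, protocol section 5.1: "Clear signs of localization of nervous system, NIHSS score 4 to 22". SAP section 4.5.1 gives "national institutes of health stroke scale (NIHSS) ≥4 and <22".
- Minimisation factor, protocol section 11.4.1: "NIHSS Score: 4–7 points, 8–14 points, 15–22 points". The same bands define the NIHSS subgroups in SAP section 7.5.2.
- First secondary endpoint, protocol section 7.1.2: "proportion of patients with NIHSS ≤1 or NIHSS improved by 4 points or more". Protocol section 9.1.2 and SAP section 5.2 also compare the change in NIHSS as a continuous score.

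**The concern.** The table prints the reading that the Overview calls a mistake. An assessor who works from the table, as instructed, gives the Overview's own example patient 1 point. An assessor who follows the Overview gives 2. Nothing elsewhere in the protocol settles which text governs, and the SAP uses NIHSS cut-offs without any item-level rule.

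The NIHSS total is compared with fixed cut-offs for entry, for the minimisation factor and for the first secondary endpoint. At a cut-off, one point decides whether a patient enters, which stratum is used and whether the patient counts as a responder. With 50 planned centres (protocol section 4.2), the convention may differ between sites. If one patient is scored by different rules at two visits, unchanged ataxia shows up as a false one-point change.

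**Working it through.** **1. The plan's own figure.** The Overview's example is ataxia of the right arm and right leg.
- Limb rule (Overview): two ataxic limbs give 2. This reproduces the stated 2 points.
- Side rule (table): one side affected gives 1. This does not.

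**2. Where the rules differ.** Take four limbs, each ataxic or not, which gives 2⁴ = 16 patterns.
- Limb rule: score = min(2, number of ataxic limbs). The cap at 2 is taken from the table's top level; the Overview does not spell out three or four limbs.
- Side rule: score = number of sides with at least one ataxic limb.

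| Pattern | Patterns | Limb rule | Side rule |
|---|---|---|---|
| None | 1 | 0 | 0 |
| One limb | 4 | 1 | 1 |
| Arm and leg, same side only | 2 | 2 | 1 |
| Two limbs, one on each side | 4 | 2 | 2 |
| Three or four limbs | 5 | 2 | 2 |

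The rules disagree in 2 of 16 patterns, always by one point. These are counts of patterns, not of patients.

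**3. Baseline decisions.** Let X be the total of the other NIHSS items for a patient with arm-and-leg ataxia on one side only. The total is X + 2 by the limb rule and X + 1 by the side rule.

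| X | Limb total | Side total | What changes |
|---|---|---|---|
| 2 | 4 | 3 | Eligible or not |
| 6 | 8 | 7 | Stratum 8–14 or 4–7 |
| 13 | 15 | 14 | Stratum 15–22 or 8–14 |
| 20 | 22 | 21 | Crosses the SAP's upper limit only |
| 21 | 23 | 22 | Not eligible or eligible (protocol limit) |

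For every other X, neither eligibility nor stratum changes.

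**4. Responder status at 90 days.** A responder has a final total ≤1 or a fall ≥4. Let Y be the total of the other items at Day 90. Assume the same rule at both visits, protocol eligibility under both rules (X from 3 to 20), and no worsening on the other items (Y from 0 to X). The number of (X, Y) combinations is the sum of (X + 1) for X = 3 to 20, which is 225.

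- *Ataxia unchanged.* Both rules give a fall of X − Y. They can disagree only when the final total is 2 by limb and 1 by side (Y = 0) and the fall is under 4. That leaves X = 3: 5 to 2 by limb (fall 3, final above 1, non-responder) and 4 to 1 by side (responder). One combination of 225.
- *Ataxia resolved.* The falls are X + 2 − Y and X + 1 − Y. They disagree when these equal 4 and 3 and the final total exceeds 1. For example, 6 to 2 by limb is a responder and 5 to 2 by side is not. 17 combinations of 225.
- *Ataxia reduced to one limb.* The final total is Y + 1 by both rules, so the limb-rule fall is again one point larger. 17 combinations of 225.

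The combinations are not equally likely, so these fractions are not patient proportions. The continuous NIHSS change also differs by one point whenever the two-limb ataxia resolves or falls to one limb.

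**The case against.** The best defence is that the Overview is unambiguous. It singles out item 7, gives a worked example and names the wrong reading. Appendix 4 also requires assessors to hold an NIHSS certificate and asks for the same assessor at baseline and at 3 months. Secondary indicators are analysed by the primary method, CMH controlling for centre (protocol section 12.2.3, SAP section 6.2.4), so a convention that varies between centres is compared within centre. Item 7 also scores 0 when the patient cannot comprehend or has limb paralysis, which narrows the group further.

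Most of this stands as a limit on the consequences. It does not remove the contradiction: the appendix also directs assessors to the table, certification does not say which page governs, and the same-assessor rule works within patients rather than across centres. The examples at the cut-offs arise even when one rule is applied consistently.

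Four stronger readings are tempting and are not supported:
- *A sizeable share of the trial is affected.* Assuming a prevalence of 5% to 15% would give 98 to 295 of 1,968 patients. The documents give no prevalence, and such a count would be of totals that differ by a point, not of decisions that change.
- *Anyone left with only one-sided arm-and-leg ataxia changes responder status.* The endpoint has a second route. With that ataxia unchanged since baseline, a limb-rule baseline of 6 or more gives a fall of at least 4 to a final 2, and the matching side-rule course ends at 1, so both rules call the patient a responder.
- *The NIHSS treatment difference is diluted by a known amount.* Nothing in the documents shows this. A rater who keeps to either rule is using a slightly different scale, which does not by itself establish attenuation.
- *Sites record the score on this very table.* The case report form's scoring sheet is not in the documents.

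**Conclusion.** The contradiction is real and in the current text: the example patient scores 2 by the Overview and 1 by the table. Its reach is narrow. It is one point, only for arm-plus-leg ataxia confined to one side. Under the protocol limits it matters for entry only when the other items total 2 or 21, and for stratum or subgroup only at 6 or 13. It matters for responder status only in the borderline courses shown above. How many patients this involves cannot be computed from the documents.

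The primary endpoint (mRS ≤1) is not scored from the NIHSS, and its CMH test controls for centre rather than NIHSS stratum, so it is touched only through eligibility and stratification. With assessors blinded, the error should not favour either arm. The conclusion assumes that the limb rule is capped at 2 and, for the responder examples, that one rule is used at both visits. The correction should be made because the score feeds three uses with hard cut-offs and the repair is cheap, not because the trial's main result is at risk.

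**What to change.** Change the item 7 table to match the Overview: 0 = absent, 1 = one limb, 2 = two or more limbs. The words *or more* are needed so that ataxia in three or four limbs has a score. With one unit in both places, the disagreement falls from 2 of 16 patterns to none. Issue the corrected sheet with a short training note to all centres, for use at every visit.

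The cost is one appendix page, one scoring sheet and the note. The differing upper NIHSS limits (22 included in the protocol, excluded in the SAP) are a separate discrepancy that this change does not resolve.
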